5.3 FURTHER ENDPOINTS

[REDACTED]

[REDACTED]

Safety and tolerability endpoints

Section 2.2.2.2 of the CTP:

Safety and tolerability of Nintedanib will be assessed based on:

- *Adverse events (including clinically relevant findings from the physical examination)*
- *Safety laboratory tests*
- *12-lead ECG*
- *Vital signs (blood pressure, pulse rate)*

5.4 OTHER VARIABLES

Section 5.2.1 of the CTP:

At screening, the medical examination will include demographics, height and body weight, smoking and alcohol history (results not mandatory to be entered into CRF or to be reported), relevant medical history and concomitant therapy, review of inclusion and exclusion criteria, review of vital signs (BP, PR), 12-lead ECG, laboratory tests (including drug screening), and a physical examination. At the end of trial examination, it will include review of vital signs, 12-lead ECG, laboratory tests, and a physical examination including determination of weight.

Age [years] will be determined as the difference between year of informed consent and year of birth.

BMI will be calculated as weight [kg] / (0.01 * height [cm])².

6. GENERAL ANALYSIS DEFINITIONS

6.1 TREATMENTS

For basic study information on treatments to be administered, assignment of treatment groups, selection of doses, refer to CTP Sections 3 and 4.

The study was originally planned to consist of up to three trial parts aiming to assess and optimize different modified release (MR) formulations of oral Nintedanib.

Section 3.1 of the CTP:

The study will be performed in healthy male subjects as an open-label, randomised, single-dose study in up to three trial parts in order to compare each of the test treatments (MR1, MR2, MRX) to the respective reference treatment R. The subjects will be randomly allocated to three treatment sequences in trial part 1 and 2 (Latin square design) and two sequences in trial part 3 (optional). There will be a washout period of at least 14 days between the treatments, i.e. the morning dose in the preceding treatment period and the morning dose in the following treatment period are separated by at least 14 days.

Each trial part was planned as a randomised crossover trial, details are provided below:

In trial part 1, it was planned to assign 30 healthy male subjects to two parallel groups (trial part 1A and 1B, each n=15). In each parallel group, subjects were randomised to one of three treatment sequences:

Trial part 1A (Cohort 1):

R / MR1-1 / MR1-2
MR1-2 / R / MR1-1
MR1-1 / MR1-2 / R

Trial part 1B (Cohort 2):

R / MR2-1 / MR2-2
MR2-2 / R / MR2-1
MR2-1 / MR2-2 / R

For details of dosage and formulation see [Table 6.1: 1](#) below:

Table 6.1: 1 Treatments and labels used in the analysis – Part 1

Trial Part	Cohort	Treatment	Short label
1A / 1B	1 / 2	C / F Ofev® [REDACTED] mg soft capsules (IR)*, [REDACTED] mg (1 capsule) twice per day (b.i.d.)	R
1A	1	A Nintedanib MR1 ¹ , Prototype 1 Tablet (MR1-1), [REDACTED] mg (1 tablet) as single dose	MR1-1
1A	1	B Nintedanib MR1 ¹ , Prototype 2 Tablet (MR1-2), [REDACTED] mg (1 tablet) as single dose	MR1-2
1B	2	D Nintedanib MR2 ² , Prototype 1 Tablet (MR2-1), [REDACTED] mg (1 tablet) as single dose	MR2-1
1B	2	E Nintedanib MR2 ² , Prototype 2 Tablet (MR2-2), [REDACTED] mg (1 tablet) as single dose	MR2-2

* Immediate Release

¹ MR1 = Monolithic Nintedanib Modified Release Prototype Tablet

² MR2 = Polyox Nintedanib Modified Release Prototype Tablet

If the trial was to be continued with trial part 2, it was planned to assign 15 healthy male subjects to the three treatment sequences:

R / MRX-1 / MRX-2
 MRX-2 / R / MRX-1
 MRX-1 / MRX-2 / R

If the trial was to be continued with trial part 3, it was planned to assign 14 healthy male subjects to the two treatment sequences:

R / MRX-5, MRX-5 / R

The trial was prematurely terminated during trial part 1 (see [Section 4](#)). General definitions, analysis definitions and description of the statistical analysis in the following sections of this document refer to the analysis of trial part 1 only.

Section 1.2.5 of the CTP:

The Residual Effect Period (REP) is the period after the last dose with measurable drug levels and/or pharmacodynamic effects still likely to be present.

For this trial using 1 day treatment of [REDACTED] to (potentially) [REDACTED] mg Nintedanib in healthy male volunteers, a REP of 14 days is used, i.e. the individual subject's end of trial is on day 15 following dosing at the earliest and the washout between periods is at least 2 weeks (see CTP Flow Chart).

Based on this, the following study phases will be defined for the analysis of adverse events (AEs):

- **Screening**
 - Ranging from 0:00h on day of informed consent until administration time of first drug administration in treatment period 1.
- **On treatment** (labelled (in Part 1): “**R**”, “**MR1-1**”, “**MR1-2**”, “**MR2-1**”, “**MR2-2**”)
 - Ranging from the administration time of first respective drug administration in this period until 14 days (12 AM on day 14) thereafter OR until next drug administration of the following period, whatever occurs first.
- **Follow-up** (labelled “**F/U R**”, “**F/U MRX-Y**”, with X=1,2, Y=1,2))
 - Ranging from 14 days (12 AM on day 14) after administration time of first drug administration of that period until the next drug administration of the following period OR until trial termination, whatever occurs first.

Section 7.3.4 of the CTP:

Note that AEs occurring after the last per protocol contact but entered before final database lock will be reported to Pharmacovigilance only and will not be captured in the trial database.

The following AE displays will be provided in the report:

In Section 15.3 and Appendix 16.1.13.1.8 (for ClinicalTrials.gov and EudraCT only) of the CTR displays, the on treatment phase will be analysed (labelled with the short label of the study treatment). The screening and follow-up phases will not be included in this analysis.

The following totals will be provided in addition for Section 15.3:

- a total over all on treatment phases from cohort 1 (“**Total Cohort 1**”)
- a total over all on treatment phases from cohort 2 (“**Total Cohort 2**”)
- a total over all on treatment phases from trial part 1 (“**Total**”)

In Section 15.4 and Appendix 16.2 (Listings) of the CTR displays, the screening period, as well as the follow-up phases will additionally be included and no totals will be provided.

For detailed information on the handling of the treatments refer to Technical TSAP ADS (analysis data set) plan and Analysis Data Reviewers guide.

6.2 IMPORTANT PROTOCOL DEVIATIONS

Data discrepancies and deviations from the CTP will be identified for all treated subjects. Consistency check listings (for identification of deviations of time windows) and a list of protocol deviations (e.g. deviations in drug administration, in blood sampling times, etc.) will be provided to be discussed at the Report Planning Meeting (RPM). At this meeting, all manual deviations identified at the sites by the CRAs and deviations too complex to program will be reviewed by the trial team to decide which are considered important. For definition of

important protocol deviations (iPD), and for the process of identification of these, refer to the Boehringer Ingelheim (BI) SOP "Identify and Manage Important Protocol Deviations (iPD)" ([2](#)).

Section 7.3 of the CTP:

Important protocol deviation (iPD) categories will be suggested in the DV domain sheet, iPDs will be identified no later than in the Report Planning Meeting, and the iPD categories will be updated as needed.

If any iPDs are identified, they are to be summarised into categories and will be captured in the iPD specification file (DV domain) ([3](#)) and in the decision log ([4](#)). The iPD specification file will be stored within the TMF in EDMS.

The iPDs will be summarized and listed in the CTR.

6.3 SUBJECT SETS ANALYSED

Section 7.3 of the CTP:

Statistical analyses for each crossover part will be based on the following analysis sets:

- *Treated set (TS): The treated set includes all subjects who were randomised and treated with at least one dose of study drug. The treated set will be used for safety analyses.*
- *Pharmacokinetic parameter analysis set (PKS): This set includes all subjects in the treated set (TS) who provide at least one PK endpoint that was defined as primary or secondary and was not excluded due to a protocol deviation relevant to the evaluation of PK or due to PK non-evaluability (as specified in the following subsection 'Pharmacokinetics'). Thus, a subject will be included in the PKS, even if he/she contributes only one PK parameter value for one period to the statistical assessment. Descriptive and model based analyses of PK parameters will be based on the PKS.*

(...)

Pharmacokinetics

Plasma concentration data and parameters of a subject will be included in the statistical pharmacokinetic (PK) analyses if they are not flagged for exclusion due to a protocol deviation relevant to the evaluation of PK (to be decided no later than in Report Planning Meeting) or due to PK non-evaluability (as revealed during data analysis, based on the criteria specified below). Exclusion of a subject's data will be documented in the CTR.

Relevant protocol violations may be

- *Incorrect trial medication taken, i.e. the subject received at least one dose of trial medication the subject was not assigned to*
- *Incorrect dose of trial medication taken*
- *Use of restricted medications*

Plasma concentrations and/or parameters of a subject will be considered as non-evaluable, if for example

- *The subject experiences emesis at any time during the labelled dosing interval.*
- *A predose concentration is >5% C_{max} value of that subject*
- *Missing samples/concentration data at important phases of PK disposition curve*

Plasma concentration data and parameters of a subject which is flagged for exclusion will be reported with its individual values but will not be included in the statistical analyses.

Descriptive and inferential statistics of PK parameters will be based on the PKS.

Only concentration values within the validated concentration range and actual sampling times will be used for the calculation of pharmacokinetic parameters. Concentrations used in the pharmacokinetic calculations will be in the same format provided in the bioanalytical report, (that is, to the same number of decimal places provided in the bioanalytical report).

Table 6.3: 1 Subject sets analysed

Class of endpoint	Subject analysis set	
	TS	PKS
Analyses of PK endpoints		X
Disposition	X	
Demographic/baseline parameters	X	
Important protocol deviations	X	
Exposure	X	

6.5 POOLING OF CENTRES

This section is not applicable, because the study was performed in only one centre.

6.6 HANDLING OF MISSING DATA AND OUTLIERS

Handling of missing data and outliers will be performed as described in the CTP, Section 7.5.

Missing or incomplete AE dates are imputed according to BI standards (see BI-KMED-BDS-HTG-0035) ([5](#)).

Missing data and outliers of PK data are handled according to BI standards (see BI-KMED-TMCP-MAN-0012 ([6](#)) and BI-KMED-TMCP-MAN-0014 ([7](#))).

6.7 BASELINE, TIME WINDOWS AND CALCULATED VISITS

The baseline value is defined as the last measurement before drug administration in each treatment period.

Section 6.1 of the CTP:

Exact times of measurements outside the permitted time windows will be documented. The acceptable time windows for screening, the end of trial examination, and measurements and assessments scheduled to occur 'before' trial medication administration in the morning of Day 1 are provided in the CTP Flow Chart.

If not stated otherwise in the CTP Flow Chart, the general acceptable deviation from the scheduled time for vital signs, ECG, and laboratory tests will be ± 30 min.

The acceptable deviations from the nominal urine sampling time points for urinalysis are:

- The pre-dose urine sample will be the first void of the day or a sample collected ≤ 3 h before dosing*
- Post-dose urine samples will be taken ± 2 h from the nominal urine sampling time*

Adherence to time windows will be checked via the consistency check listings at the RPM.

Unscheduled measurements of laboratory data and vital signs data will be assumed to be repeat measurements of the most recent scheduled measurement (e.g. for follow-up or confirmation of a particular value). Therefore, unscheduled measurements will be assigned to the planned time point of the previous scheduled measurement.

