7. PLANNED ANALYSIS

Each of the three possible trial parts was planned to be analysed separately. Cohort 1 and cohort 2 of trial part 1 will be presented in one table, but the reference group will be stratified to R (Cohort 1) and R (Cohort 2).

Safety analysis (refer to [Section 7.8](#)) will be performed by [REDACTED] and will be presented in Sections 15.1 to 15.4 of the CTR and in Appendix 16.2 and 16.1.13.1.

Inferential statistical analyses of PK endpoints (refer to [Section 7.4](#) and [Section 7.5.2](#)) will also be performed by [REDACTED] and will be presented in Section 15.5 of the CTR and in Appendix 16.1.13.3.

Descriptive data analysis of PK endpoints and concentrations will be performed by the department of Translational Medicine and Clinical Pharmacology (TMCP) at BI and will be presented in Section 15.6 of the CTR and in Appendix 16.1.13.5.

The format of the listings and tables will follow the BI standards (see BI-KMED-BDS-HTG-0045 [\(8\)](#)) with the exception of those generated for PK-calculations following BI standards for PK/PD analysis [\(9\)](#).

The individual values of all subjects will be listed, sorted by treatment sequence, subject number and visit. The listings will be included in Appendix 16.2 of the CTR.

For end-of-text tables, the set of summary statistics for non-PK parameters is:

N	number non-missing observations
Mean	arithmetic mean
SD	standard deviation
Min	minimum
Median	median
Max	maximum

For analyte concentrations and PK parameters, the following descriptive statistics will additionally be calculated:

Nobs	number of observations
CV	arithmetic coefficient of variation
gMean	geometric mean
gCV	geometric coefficient of variation
P10	10th percentile
Q1	1st quartile
Q3	3rd quartile
P90	90th percentile

The data format for descriptive statistics of concentrations will be identical to the data format of the respective concentrations. The descriptive statistics of PK parameters will be calculated using the individual values with the number of decimal places as provided by the evaluation

program. Then the individual values as well as the descriptive statistics will be reported with three significant digits in the CTR.

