7.8.1 Adverse Events

AEs will be coded using MedDRA. The coding version number will be displayed as a footnote in the respective output.

Unless otherwise specified, the analyses of AEs will be descriptive in nature. All analyses of AEs will be based on the number of subjects with AEs and NOT on the number of AEs. BI standards as presented in “Analysis and Presentation of Adverse Event Data from Clinical Trials – Display Template” [BI-KMED-BDS-HTG-0041] ([11](#)) and [BI-KMED-BDS-HTG-0066] ([12](#)) will be applied.

The analysis of AEs will be based on the concept of treatment emergent AEs. That means that all AEs will be assigned to ‘screening’, ‘on-treatment’ or ‘follow-up’ phases as defined in [Section 6.1](#). The ‘on-treatment’ and ‘follow-up’ AEs will be analysed based on actual treatments, as defined in [Table 6.1: 1](#).

According to the clinical study protocol, adverse events of special interest (AESI) will be analysed:

Section 5.2.6.1.4 of the CTP:

The following are considered as AESIs:

- Hepatic injury
A hepatic injury is defined by the following alterations of hepatic laboratory parameters:
 - o *An elevation of AST (aspartate transaminase) and/or ALT (alanine transaminase) ≥ 3 -fold ULN combined with an elevation of total bilirubin ≥ 2 -fold ULN measured in the same blood sample, or*
 - o *Aminotransferase (ALT, and/or AST) elevations ≥ 10 fold ULN*

These lab findings constitute a hepatic injury alert and the subjects showing these lab abnormalities need to be followed up according to the ‘DILI checklist’ provided in the ISF. In case of clinical symptoms of hepatic injury (icterus, unexplained encephalopathy, unexplained coagulopathy, right upper quadrant abdominal pain, etc.) without lab results (ALT, AST, total bilirubin) available, the Investigator should make sure that these parameters are analysed, if necessary in an unscheduled blood test. Should the results meet the criteria of hepatic injury alert, the procedures described in the DILI checklist should be followed.

According to ICH E3 ([13](#)), in addition to Deaths and serious adverse events, ‘other significant’ AEs need to be listed in the clinical trial report. These will be any non-serious

adverse event that led to an action taken with study drug (e.g. discontinuation or dose reduced or interrupted).

An overall summary of adverse events will be presented.

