7.8.2 Laboratory data

The analyses of laboratory data will be descriptive in nature and will be based on BI standards [BI-KMED-BDS-HTG-0042] (14). Analyses will be based on normalised values.

Laboratory data will be analysed qualitatively via comparison of laboratory data to their reference ranges. Values outside the reference range as well as values defined as possibly clinically significant will be flagged in the data listings.

Clinically relevant findings in laboratory data will be reported as baseline conditions (at screening) or as AEs (during the trial) if judged clinically relevant by the investigator, and will be analysed as such.

It is the investigator's responsibility to decide whether a lab value is clinically significantly abnormal or not (at the RPM at the latest).

Descriptive statistics of laboratory data including change from baseline will be calculated by planned time point based on the worst value of the subject at that planned time point (or assigned to that planned time point).

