7.8.3 Vital signs

Descriptive statistics over time including change from baseline will be performed for vital signs (blood pressure and pulse rate). In the listing the change from baseline will also be displayed.

For vital signs, descriptive statistics will be calculated by planned time point based on the last value of the subject at that planned time point (or assigned to that planned time point). Time courses of vital signs presenting means and standard deviations per time point and treatment group will be provided.

Clinically relevant findings will be reported as baseline conditions (at screening) or as AEs (during the trial) if judged clinically relevant by the investigator, and will be analysed as such.

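### SAP 6.7 carries unscheduled values back past the morning dose, so a post-dose lab (before 24 h) or vital sign (before 2 h) is tabulated as pre-dose

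*SAP*

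**What the plan says.** SAP 6.7 starts from an assumption: "Unscheduled measurements of laboratory data and vital signs data will be assumed to be repeat measurements of the most recent scheduled measurement". It concludes that "unscheduled measurements will be assigned to the planned time point of the previous scheduled measurement". Neither sentence mentions dosing. The same section defines baseline separately: "The baseline value is defined as the last measurement before drug administration in each treatment period".

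The summary tables then use the assigned time point. SAP 7.8.2 computes lab statistics "based on the worst value of the subject at that planned time point (or assigned to that planned time point". SAP 7.8.3 computes vital-sign statistics "based on the last value of the subject at that planned time point (or assigned to that planned time point". It also adds figures: "Time courses of vital signs presenting means and standard deviations per time point and treatment group will be provided".

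Both protocol flow charts place the Day 1 safety labs and vital signs at about -1:30, and footnote 2 requires them to be finished before dosing. After the morning dose, the next safety labs are at 24 h and 72 h, and the next vital signs at 2, 4, 24 and 72 h. The 'visit 2 only' label in the -1:30 row is read here as applying to treatment allocation, because Protocol 5.2.3 requires lab set B at Visits 2, 3 and 4.

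**The concern.** Treating an unscheduled value as a repeat of the last scheduled one is reasonable when nothing has happened in between. It is not reasonable when the subject has taken the study drug in between, because the value then describes a treated subject. Under SAP 6.7 such a value is still placed in the pre-dose row.

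The SAP itself foresees a case that is not a repeat. For symptoms of hepatic injury without available results, SAP 7.8.1 says that "the Investigator should make sure that these parameters are analysed, if necessary in an unscheduled blood test". That case is exceptional, but the test is a new measurement prompted by a new event.

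At stake is the contrast between pre-dose and post-dose in the safety summaries. A value taken after dosing can alter the pre-dose row and be absent from every post-dose row.

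**Working it through.** The plan gives no figure to reproduce, so the check applies the rule to the schedule.

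**Inputs**
- Scheduled labs (flow charts): -1:30, 24:00, 72:00 h.
- Scheduled vital signs (flow charts): -1:30, 2:00, 4:00, 24:00, 72:00 h.
- Rule (SAP 6.7): assigned time = latest scheduled time at or before the actual time.
- Subjects analysed (SAP 4): 7 in cohort 1 and 14 in cohort 2.
- Columns (SAP 7): "the reference group will be stratified to R (Cohort 1) and R (Cohort 2"), so no column pools the two cohorts.

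**Step 1: where an unscheduled value lands**

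| Actual time after morning dose | Lab assigned to | Vital sign assigned to |
|---|---|---|
| 0.5, 1, 1.9 h | pre-dose | pre-dose |
| 3 h | pre-dose | 2 h |
| 6, 12, 23 h | pre-dose | 4 h |
| 25 h | 24 h | 24 h |

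The affected window is 0–24 h for labs (24/72 = 33.3% of the 72 h in-house period after dosing) and 0–2 h for vital signs (2/72 = 2.8%). Later unscheduled values, including reference-arm vital signs after the 12 h dose, already fall in a row that follows the morning dose and are not part of this point.

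**Step 2: what the tables do with it**
- Vital signs use the last value, so the post-dose reading always replaces the true pre-dose reading.
- Labs use the worst value, so the post-dose result replaces the true one when it is worse. When it is not worse, it drops out of the by-time-point table.
- In both cases the value enters no post-dose row.

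Protocol 7.3.4 does not correct this, because it attributes measurements to treatment by planned time and not by actual time.

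**Step 3: size**

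If k displaced values in a column of n subjects differ from the true pre-dose values by d on average, then

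shift in pre-dose mean = (k/n) × d.

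| k | n = 7 (cohort 1) | n = 14 (cohort 2) |
|---|---|---|
| 1 | 1/7 = 14.3% of d | 1/14 = 7.1% of d |
| 2 | 2/7 = 28.6% of d | 2/14 = 14.3% of d |

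These are minimum shares, since a column with fewer subjects gives a larger one. For labs they apply only when the later value is the worse one. The documents give neither k nor d, and none is assumed.

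**The case against.** Five arguments can be made in the plan's favour.

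1. **The baseline definition may protect the pre-dose row.** If that row is simply the baseline, a post-dose value cannot enter it. But the definition governs baseline. The by-time-point rows follow SAP 7.8.2 and 7.8.3, which expressly admit assigned values. On the text as written, the pre-dose row and the baseline could disagree.
2. **Unseen documents may hold an exception.** The table shells, the internal lab standard and the analysis data set plan are not available here. This stands as a limit: the rule in SAP 6.7 has no exception, but the programmed output could differ.
3. **Early vital signs will be rare.** Protocol 5.2.2 requires supine rest, while Protocol 4.1.4 forbids lying down for 2 h after each dose. Protocol 6.1 also lets the 2 h reading be taken up to 30 min early, which shortens the window. This makes the vital-sign case uncommon but not impossible, and it leaves the lab window of about 24 h untouched.
4. **No safety signal is lost.** Adverse events are assigned by onset time, hepatic injury alerts have their own table, individual values are listed and out-of-range labs are flagged. This is correct, and it confines the problem to descriptive tables and figures.
5. **The remedy has a price.** A separate row would mix times and might hold no subject or one. A genuine confirmatory retest drawn after the dose would also leave the pre-dose row. Both are true. The second is accepted because such a sample no longer shows the untreated state.

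**Conclusion.** The point holds. Read with the flow charts, SAP 6.7 places an unscheduled lab from the first 24 h after the morning dose, or a vital sign from the first 2 h, in the pre-dose row. This is a stated rule that gives a wrong tabulation, not a missing detail.

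One such value moves a pre-dose mean by at least 14.3% (cohort 1) or 7.1% (cohort 2) of its difference from the true value. The absolute effect is unknown, because the number of such values is not reported and may be zero.

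The effect is limited to the by-time-point lab and vital-sign summaries and the vital-sign time courses. Baseline as defined, the PK endpoints, adverse event counts, listings and lab flags do not change. The conclusion assumes that pre-dose labs and vital signs are taken in every period and that no unseen standard overrides SAP 6.7.

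**What to change.** Add one sentence to SAP 6.7: an unscheduled lab or vital sign taken after the morning dose of a period is not carried back to that period's pre-dose time point. Summarise it, for labs and vital signs alike, in a separate 'unscheduled post-dose' row under that period's treatment. Do not move it forward to the 24 h row (labs) or the 2 h row (vital signs). Leave the row out of the vital-sign time-course figures, because it has no single planned time. All other unscheduled values keep the present rule.

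The cost is that sentence and a small programming change, with no new data. The downside is one extra row in the lab and vital-sign tables, which may be sparse.
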